An Interactive Response Technology (IRT) system will be utilized to register subjects. Once the subject has signed the informed consent the site will obtain a screening (subject) number via the IRT system. Once the screening number is assigned, if the subject is not enrolled into the study, the reason for screen failure will be documented in the source document and will be captured in the eCRF.

The results of all screening evaluations must be within clinically acceptable limits, upon review by the investigator before a subject can be administered study drug. Subjects will not be enrolled in the study if laboratory or other screening results are unacceptable.

Subjects who complete all screening procedures and meet the eligibility criteria in Section 5.2.1 and none of the exclusion criteria in Section 5.2.2 will proceed to enrollment.

Post-Treatment Follow-Up Visit(s)

For subjects who discontinue study treatment for reasons other than disease progression, the following post-treatment assessments will be performed every 12 weeks (\pm 1 week) until criteria are met for discontinuation from the study (e.g., disease progression, death or a subject's refusal of the Post-Treatment visits) for a period of 1 year after last subject's last dose or possibly sooner if all patients have discontinued and most patients have expired:

- Hematology
- Disease Assessment

Survival Assessment(s)

Survival information (e.g., date and cause of death, post-treatment cancer therapies, including transplantation) will be collected once the subject's disease has progressed via telephone calls (e.g., to subject or family member) and/or clinical visits at 12 weeks intervals (\pm 1 week) after the subject's last study visit for a period of 1 year after last subject's last dose or possibly sooner if all patients have discontinued and most patients have expired.

5.3.1.2 Confinement

Subjects will be hospitalized during dose escalation of venetoclax. Confinement is recommended to begin by Study Day -1 and must occur by at least Day 1 through at least 24 hours after completion of the ramp-up period for subjects in both Phase 1 and Phase 2 including Cohort C.

5.3.1.3 Meals and Dietary Requirements

Each dose of venetoclax will be taken with approximately 240 mL of water within 30 minutes after the completion of a meal, preferably breakfast.

Subjects may not consume grapefruit or grapefruit products, Seville oranges (including marmalade containing Seville oranges) or Starfruit within the 3-day period prior to the first study drug administration and until the last day of treatment is completed due to possible CYP3A mediated metabolic interaction.

5.3.1.4 Blood Samples for Pharmacogenetic Analysis

A 4 mL whole blood sample for DNA isolation will be collected on Cycle 1 Day 1, Cycle 4 Day 1, and the Final Visit. The sample collection tubes will minimally be labeled with "PG-DNA," protocol number, visit, and subject number. Pharmacogenetic collection should occur unless precluded by local or national regulations or policies. AbbVie will store the DNA samples in a secure storage space with adequate measures to protect confidentiality. The samples will be retained while research on venetoclax (or drugs of this class) continues but no longer than 20 years. Sample collection and shipping information are detailed in the most current version of Study M14-387 Laboratory Manual.

5.3.1.5 Pharmacodynamic and Predictive Biomarker Testing

Blood Collections

Whole blood will be collected into appropriately labeled tubes and processed as outlined in the most current version of Study M14-387 Laboratory Manual.

Blood Collection for Mutational Profiling:

Approximately 2.5 mL for blood will be collected prior to dose at:

- Screening (preferred) or prior to the first dose of study drug
- Final Visit/Time of Relapse

Blood Collection for Plasma

Approximately 4 mL of blood or 12 mL of blood will be collected prior to dose at

- Screening (preferred) or prior to the first dose of study drug (4 mL blood)

- Cycle 2 Day 1 (4 mL blood)
- Response assessments:
Cycle 4 Day 1, and every 3 cycles thereafter (12 mL blood)
Subjects who achieve 2 consecutive CR assessments and no longer require a bone marrow aspirate/biopsy for disease assessment, will still have plasma and serum collections at every 3 cycles thereafter.
- Final Visit/Time of Relapse (4 mL blood)

Blood Collection for Serum

Approximately 3.5 mL of blood will be collected prior to dose at

- Screening (preferred) or prior to the first dose of study drug
- Cycle 2 Day 1
- Response assessments:
Cycle 4 Day 1, and every 3 cycles thereafter
Subjects who achieve 2 consecutive CR assessments and no longer require a bone marrow aspirate/biopsy for disease assessment, will still have plasma and serum collections at every 3 cycles thereafter.
- Final Visit/Time of Relapse

Blood Collection for Ex Vivo Sensitivity and Translational Research (e.g., mutational analysis, BH3 profiling):

Approximately 8 mL of blood will be collected prior to dose at:

- Screening (preferred) or prior to the first dose of study drug
- Cycle 2 Day 1
- Final Visit/Time of Relapse

Blood Collection for Bcl-2 Family Protein Analysis

Approximately 2 ml of blood will be collected prior to dose at:

- Screening (preferred) or prior to the first dose of study drug
- Cycle 2 Day 1
- Final Visit/Time of Relapse

Bone Marrow Aspirate and Biopsy Collections

Bone marrow aspirates should be drawn into appropriately labeled tubes in conjunction with the clinical assessments. A portion of the aspirate must be processed according to the institutional standard procedures for diagnostic evaluation; however, approximately 6 to 8 mL of the bone marrow aspirate should be collected for biomarker assessments. Subjects, who achieve 2 consecutive CR assessments and no longer require a bone marrow aspirate/biopsy for disease assessment, will also not require bone marrow aspirates for biomarker collections. Detailed processing will be as outlined in the most current version of the Study M14-387 Laboratory Manual for the following:

Minimal Residual Disease Assessment

Minimal Residual Disease Assessment aspirate samples will be collected, processed and shipped to the central laboratory per the most current version of the Study M14-387 Laboratory Manual.

NOTE: This should be the first tube drawn from the bone marrow aspirate collection.

- Screening (preferred) or prior to the first dose of study drug
- Cycle 2 Day 1
- Response assessments: Cycle 4 Day 1, and every 3 cycles thereafter
- Final Visit/Time of Relapse

Mutational Profiling

Mutational Profiling will be collected at:

- Screening (preferred) or prior to the first dose of study drug
- Final Visit/Time of Relapse

Bcl-2 Family Protein Analysis

Bcl-2 Family Protein Analysis will be collected at:

- Screening (preferred) or prior to the first dose of study drug
- Cycle 2 Day 1
- Final Visit/Time of Relapse

Ex vivo sensitivity and Translational Research (e.g., BH3 profiling)

Ex vivo sensitivity and Translational research will be collected at:

- Screening (preferred) or prior to the first dose of study drug
- Cycle 2 Day 1
- Final Visit/Time of Relapse

Bone Marrow Core Biopsy for Bcl-2 IHC

A portion of the core biopsy (applicable only to counties/individual sites where this procedure is included as standard of care) must be processed for according to the institutional standard procedures for diagnostic evaluation: however, if tissue remains approximately 4 to 10 slides from the biopsy should be collected for immunohistochemistry analysis at:

- Screening (preferred) or prior to the first dose of study drug
- Final Visit/Time of Relapse

5.3.2 Drug Concentration Measurements

5.3.2.1 Collection of Samples for Analysis

The timing of PK blood collections will take priority over all other scheduled study activities except for dosing. The order of blood collections will be maintained to the minute such that the time intervals relative to the preceding dosing will be the same for all

subjects. The date and time of each blood sample collection will be recorded to the nearest minute on the source documents.

Blood Samples for Venetoclax Assay

Blood samples (3 mL) for venetoclax (and possible metabolite[s]) assay will be collected by central venous catheter into evacuated potassium (K₂) EDTA tubes at the following times:

Phase 1 Cohorts

- Cycle 1 Day 2: 8 hours post-dose
- Cycle 1 Days 3 – 6 or 7: 8 hours post-dose (if escalation to a new dose level)
- Cycle 1 Day 10: 0 hour (pre-dose) and at 2, 4, 6, 8 and 24 hours post-dose
- Cycle 1 Day 18: 0 hour (pre-dose) and at 2, 4, 6, 8 and 24 hours post-dose
- Cycle 2 Day 1, Cycle 4 Day 1, and every 3 cycles thereafter (\pm 7 Days): 0 hour (pre-dose)

Initial Phase 2 Cohort

- Cycle 1 Day 2, Cycle 2 Day 1, Cycle 4 Day 1, and every 3 cycles thereafter (\pm 7 Days): 0 hour (pre-dose)

Phase 2 Cohort C

- Cycle 2 Day 1, Cycle 4 Day 1, and every 3 cycles thereafter (\pm 7 Days): 0 hour (pre-dose)

A total of approximately 17 blood samples (51 mL) will be collected per subject during Cycle 1 in Phase 1 portion. For a schedule of the blood collection for venetoclax assay, refer to [Table 7](#) and [Table 8](#). All 0 hour (pre-dose) samples are relative to the start of venetoclax administration. The PK collection performed 8 hours post-dose after each dose escalation may be taken up to 1 hour prior or up to 20 minutes after to allow for processing, if necessary.

The date and time (to the nearest minute) of each venetoclax dose and whether or not the venetoclax dose was taken within 30 minutes after the completion of a meal (preferably breakfast) will be recorded on the eCRF for each scheduled venetoclax PK day and for the 2 days prior to each scheduled venetoclax PK day (if applicable). Sites will ensure all information is captured through source documents (site or subject calendar/diary provided by AbbVie).

Blood Samples for Cytarabine Assay

Blood samples (4 mL) for cytarabine assay will be collected by central venous catheter in the Phase 1 cohorts at the following times:

- Day 1 and Day 10 of Cycle 1: 0 hour (pre-dose) and at 15 and 30 minutes and 1, 3, 6 hours following the SC dose.

For a schedule of the blood collection for cytarabine assay, refer to [Table 7](#).

The start time of each cytarabine SC injection will be recorded to the nearest minute on the eCRF as applicable.

A total of 12 blood samples (72 mL) for cytarabine concentration determination are planned to be collected per subject.

The necessary anticoagulant and sample pre-treatment will be provided in the lab manual for the study. These samples are not optional, however, due to the expected complexity of the sample collection and processing for the cytarabine PK, AbbVie recognizes some centers may not have the capability to perform the PK samples. In those instances, the cytarabine PK samples will not be collected. Sites with these capabilities will be predetermined.

5.3.2.2 Handling/Processing of Samples

Blood Samples for Venetoclax PK Assay

Detailed sample collection and processing instructions for the venetoclax PK samples will be provided in the lab manual for this study.

Blood Samples for Cytarabine PK Assay

Detailed sample collection and processing instructions for the cytarabine PK samples will be provided in the lab manual for this study.

5.3.2.3 Disposition of Samples

The frozen plasma PK samples for venetoclax and cytarabine will be packed in dry ice sufficient to last during transport and shipped from the study site to the central lab according to instructions in the laboratory manual. An inventory of the samples included will accompany the package. The central lab will ship the samples to reference laboratories for analysis.

5.3.2.4 Measurement Methods

Plasma concentrations of venetoclax will be determined by the Drug Analysis Department at AbbVie using a validated method. Plasma concentrations of possible venetoclax metabolite(s) may be determined with either validated or non-validated methods. Plasma concentrations of cytarabine will be determined at an external lab using a validated method under the supervision of the Drug Analysis Department at AbbVie.

5.3.3 Efficacy Variables

Efficacy Assessments

Responses will be evaluated based on the revised guidelines by the International Working Group (IWG) for AML.³⁸ As a significant number of the subjects in this study might have antecedent hematologic illnesses, hematologic response will also be evaluated. Transfusion dependence is defined as having received ≥ 2 units of RBCs and or platelets

within 8 weeks prior to study treatment. Duration of Response will be measured from the time when all response criteria are first met until recurrent or progressive disease is documented.

Criteria for Evaluation is as follows:

- CR: Absolute neutrophil count $\geq 10^3/\mu\text{L}$, platelets $\geq 10^5/\mu\text{L}$, red cell transfusion independence, and bone marrow with $< 5\%$ blasts.
- CRi: bone marrow with $< 5\%$ blasts, and peripheral neutrophils of $< 10^3/\mu\text{L}$ or platelets $< 10^5/\mu\text{L}$.
- PR: all of the hematologic values for a CR but with a decrease of at least 50% in the percentage of blasts to 5% to 25% in the bone marrow aspirate.
- MLFS: less than 5% blasts in an aspirate and/or bone marrow core sample. There should be no blasts with Auer rods or persistence of extramedullary disease. The presence of a unique phenotype (by flow cytometry) identical to what was found in the pretreatment specimen (e.g., CD34, CD7 coexpression) should be viewed as persistence of leukemia.
- RD: failure to achieve CR, CRi, PR; only including subjects surviving at least 7 days following completion of initial treatment cycle, with evidence of persistent leukemia by blood and/or bone marrow examination.
- PD: one or more of the following: $\geq 50\%$ decrement from maximum response levels in neutrophils or platelets, a reduction in hemoglobin by at least 2 g/dL, or transfusion dependence,* not due to other toxicities and bone marrow blast $\geq 5\%$.

In addition to the response determination using the above IWG AML response criteria, each subject will also be evaluated for hematologic response and complete remission with partial hematologic recovery (CRh).

- HR: improvement in peripheral blood counts with all of the following: fewer absolute peripheral blood blasts than prior to initiating study treatment for subjects presenting with peripheral blood blasts, ANC ≥ 500 (cells/ μL),

platelets $\geq 0.25 \times 10^5$ (platelets/ μL), and no more than 2 units of packed red blood cells within a 28-day period.

- CRh: all of the following criteria are met: Bone marrow with $< 5\%$ blasts, peripheral neutrophils of $\geq 0.5 \times 10^3/\mu\text{L}$, and peripheral platelets $\geq 0.5 \times 10^5/\mu\text{L}$ **

* Transfusion independence is defined as the absence of any RBC or platelet transfusion during any consecutive 8 weeks during the treatment period.³⁹

** For a bone marrow sample collected before the last cycle of study treatment, the hematology lab results collected from the date of bone marrow sample collection up to Day 1 of a subsequent cycle of study treatment will be used for CRh analysis. For a bone marrow sample collected during or after the last cycle of study treatment, the hematology lab results collected within 14 days after bone marrow sample collection date will be used for CRh analysis.

Reporting of Results

All dosed subjects will be assessed for response to treatment based on the published guidelines. Assessments will be performed at Cycle 2 Day 1, Cycle 4 Day 1, and every 3 cycles thereafter for response assessment until two successive bone marrow samples document a CR. When additional bone marrow evaluations are routinely indicated for clinical management, additional collection of bone marrow aspirate and peripheral blood are strongly encouraged as these findings have the potential to define either remission status or potential progression of leukemia. NOTE: For subjects who achieve CR or CRi, MRD status may be determined.

Subjects will be assigned to one disease state for best IWG response assessment, achievement of protocol defined hematologic response, and minimal residual disease positivity at the time of the best response.

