8.1.3.1.7 Post Baseline Transfusion Independence (RBC/Platelet)

Post baseline transfusion independence is defined as a period of at least 56 days with no RBC or platelet transfusion between the first dose of study drug and the last dose of study drug + 30 days. Post baseline transfusion independence rate will be estimated as the portion of subjects who achieve transfusion independence post baseline. The corresponding 95% CI for transfusion independence rate will be provided based on the binomial distribution (Clopper-Pearson exact method).

In addition, the baseline transfusion dependence rate, which is defined as the portion of subjects who received either RBC or platelet transfusion within 56 days prior to the first dose of study drug, will be summarized.

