8.1.7 Overall Survival (OS)

Time to death for a given subject will be defined as the number of days from the date of first dose of study drug to the date of the subject's death. All events of death will be included, regardless of whether the event occurred while the subject was still taking study drug, or after the subject discontinued study drug. If a subject has not died on or before the "Cutoff" date, and there is any data (survival follow-up, study visit, death date, etc.) confirming that the subject is still alive or dies after the "Cutoff" date, the data will be censored at the "Cutoff" date; otherwise the data will be censored at the date when the subject was last known to be alive.

For each analysis datasets, the distribution of OS will be estimated using Kaplan-Meier methodology. Median survival time with the corresponding 95% CI will be provided from Kaplan-Meier estimation.

OS will be summarized for all subjects, subjects achieving CR, subjects achieving CRh, and non-CR/non-CRh subjects.

8.1.8 Post Baseline Transfusion Independence Rate (RBC/Platelet) and Duration of Post Baseline Transfusion Independence

The transfusion data was designed to be collected during the treatment period and until the 30 day follow-up visit. Therefore, the evaluation period for the post baseline transfusion independence is from the first dose of study drug to the last dose of study drug + 30 days, disease progression (including clinical progression), or death, whichever is earlier. Thus, post baseline transfusion independence is defined as a period of at least 56 days (≥ 56 days) with no RBC or platelet transfusion during the evaluation period.

Post baseline transfusion independence rate will be estimated as the proportion of subjects known to achieve transfusion independence during the evaluation period. The corresponding 95% CI for transfusion independence rate will be provided based on the binomial distribution (Clopper-Pearson exact method).

In addition, the baseline transfusion independence rate, which is defined as the proportion of subjects who received no transfusion within 56 days prior to the first dose of study drug (Studies M14-358 and M14-387) or 28 days (Study M14-212) prior to the first dose of study drug, will also be summarized. An analysis based on the definition of baseline transfusion independence as 28 days on or prior to the first dose of study drug will also be performed for all studies.

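### Protocol and SAP close the transfusion-independence window at different points: only the SAP stops at progression or death, and neither stops at post-treatment therapy

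*Protocol*

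**What the plan says.** **Protocol 8.1.3.1.7** defines the endpoint as "a period of at least 56 days with no RBC or platelet transfusion between the first dose of study drug"; the closing point of the window is 30 days after dosing ends. Nothing in that section ends the window at progression, death or another therapy.

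**SAP 8.1.8** keeps the 56 days. It explains that transfusions were to be recorded through the 30-day follow-up visit, and it ends the window at "the last dose of study drug + 30 days, disease progression (including clinical progression), or death, whichever is earlier". Its numerator is the "proportion of subjects known to achieve transfusion independence during the evaluation period". It has no stop at post-treatment therapy either.

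**Protocol 5.3.3** carries a footnote: "Transfusion independence is defined as the absence of any RBC or platelet transfusion during any consecutive 8 weeks during the treatment period". The asterisk belongs to the progression criterion ("or transfusion dependence,* not due to other toxicities"), not to the rate. The protocol does not say when the treatment period ends.

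Neither document says which definition governs the reported rate.

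**The concern.** Transfusion independence is a listed efficacy analysis (protocol 8.1.3, SAP 6.2). Both documents give it a Clopper-Pearson interval. The SAP also reports it by baseline transfusion status, by duration (8.1.8) and within every subgroup (8.1.13).

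Protocol 5.3.1.1 expects subjects with progression to be taken off the study, so for them most or all of the 30-day tail can follow progression. Under the protocol those days help a subject reach 56; under the SAP they do not. The same records can therefore give two rates, and the higher one reports time after treatment failure as benefit of venetoclax + LDC.

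A second gap is common to both windows. A subject who stops without progression and starts another therapy within 30 days can have transfusion-free days on that therapy credited to the study regimen.

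**Working it through.** **Inputs**
- Required run: 56 days (protocol 8.1.3.1.7, SAP 8.1.8) or 8 weeks (protocol 5.3.3). 8 × 7 = 56, so the length agrees everywhere.
- First dose is Study Day 1 (SAP 7.0), so days are counted inclusively.
- Denominators: 92 (all subjects) and 82 (600 mg), from SAP Table 3.

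**Window length.** Let L be the study day of last dose, P of progression and D of death.
- Protocol: L + 30.
- SAP: the smallest of L + 30, P and D.

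| Case | Protocol 8.1.3.1.7 | SAP 8.1.8 |
|---|---|---|
| L = P = 26 | 26 + 30 = 56 | 26 |
| L = P = 40 | 40 + 30 = 70 | 40 |
| L = P = 55 | 55 + 30 = 85 | 55 |
| L = P = 56 | 56 + 30 = 86 | 56 |
| L = 26, no progression or death | 56 | 56 |

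**Who is classified differently.** Take progression on the day of last dose, and let r be the transfusion-free run ending that day.
- Protocol: r + 30 ≥ 56, so r ≥ 26.
- SAP: r ≥ 56.

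The two disagree for r from 26 to 55, at any total length of treatment. Two conditions apply: the subject has no earlier 56-day run, and stays transfusion-free for the remaining 56 − r days (30 days if r = 26, 1 day if r = 55). Example: last transfusion Day 14, last dose and progression Day 40. Days 15 to 70 are 56 days under the protocol; Days 15 to 40 are 26 days under the SAP.

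**Direction.** The SAP window lies inside the protocol window, so on the same data the protocol rate can only equal or exceed the SAP rate.

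**Size.** Each reclassified subject moves the rate by 1/92 = 1.1 points or 1/82 = 1.2 points. The documents give no count. For scale only, an assumed 1 to 8 subjects gives 1.1 to 8.7 points (8/92) or 1.2 to 9.8 points (8/82).

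**Shortest treatment that can qualify.** L + 30 ≥ 56 gives L ≥ 26 (Day 27 if elapsed days are counted). SAP 8.1.8 gives the same day when neither progression nor death intervenes. At that minimum the subject must have no transfusion from Day 1 through Day 56.

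**Post-treatment therapy.** SAP 8.1.1 to 8.1.3 drop disease assessments made after it. Table 4 censors response duration at its start when no qualifying event has occurred. SAP 8.1.12 ends MRD data there. SAP 8.1.8 and protocol 8.1.3.1.7 do neither.

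**The case against.** The strongest reply is that the SAP already handles this. It explains the collection period, stops at progression or death, and counts only subjects known to qualify. The endpoint is not among the objectives in protocol 4.0, and SAP 9.0 plans no formal testing, so no sample size or decision rule depends on it. That limits the importance. It does not remove the conflict, because the protocol still states the longer window and nothing gives the SAP precedence. It also leaves the post-treatment therapy gap, which can affect at most the 30-day tail.

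Four stronger readings are tempting and are not supported:

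- **Three competing windows.** The 5.3.3 sentence is a footnote to the progression criterion. It is a separate third window only if the treatment period ends at last dose. The safety SAP ends that period at the final dose in 7.5 and 30 days later in 7.6.3; on the second reading, 5.3.3 matches 8.1.3.1.7.
- **The protocol section is to blame for counting subjects treated for only 26 days.** That minimum comes from the 30-day tail, which the SAP shares.
- **The protocol credits days after death.** That rests on silence in 8.1.3.1.7, not on a rule. Credit after progression is the realistic case.
- **The protocol wording is the newer and so prevails.** The protocol is dated October 2020 and efficacy SAP version 4.0 October 2019. But the itemized changes in Appendix I touch neither 5.3.3 nor Section 8, so the text was carried over and is not shown to postdate the SAP.

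**Conclusion.** The point holds for two definitions of one rate. Protocol 8.1.3.1.7 lets days after progression count towards the 56, and SAP 8.1.8 does not. Subjects who reach 56 days only through such days are classified differently, always in the direction of a higher protocol rate. Neither definition stops at post-treatment therapy, which is out of step with the SAP's handling of CR, CRh, response duration and MRD.

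The firm size is the weight of one subject, 1.1 or 1.2 points; subgroups have smaller denominators, so one subject weighs more there. A total shift in points cannot be derived, because the number of affected subjects is not in the documents. The Day 40 example assumes that progression is dated on the day of last dose; a later progression date within the tail narrows the difference. The rate is descriptive, so no error rate or power is affected.

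**What to change.** In protocol 8.1.3.1.7 and SAP 8.1.8, use one window: from first dose to the earliest of last dose + 30 days, disease or clinical progression, start of post-treatment therapy, or death. Make the 5.3.3 footnote refer to that window, or define the treatment period there.

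This does not change the 26-day minimum, because the 30-day tail stays. The sponsor should therefore state separately whether off-treatment days within the tail count towards the 56.

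The cost is wording in two protocol sections and one SAP section. The SAP already uses all the dates needed for other endpoints. The reported rate may be slightly lower.
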